8.8.1. Holding rules

Study holding rules which will be applied during the safety evaluation are defined below.

If a holding rule 1a through 1d is observed by the investigator, it will be reported promptly to GSK within 24 hours. Meeting the other holding rules will be determined by IDMC review of safety data at regular intervals.

These holding rules have been written under the assumption that safety data of all subjects will be available. Therefore, the investigator will be requested to record safety data meeting the criteria of holding rules in the eCRF within 24 hours after reception of the data to ensure that all necessary information are available for IDMC reviews. If the data from all subjects are not available, the holding rules will be assessed on a pro-rata basis.

Upon meeting of any holding rules, further vaccination will be immediately put on hold pending safety review and consultation with the GSK Biologicals' Vaccine Safety Monitoring Board (VSMB), as appropriate.

GSK Biologicals' decision on whether to suspend, modify, or continue the conduct of the study on all groups or on selected groups will be communicated to the investigators, to CBER, and to the IRBs/IECs.

In case of a safety concern, the final responsibility to recommend whether or not the trial should be stopped permanently rests with the sponsor, after having considered all the safety information available. If the trial is stopped, a letter indicating the reasons for stopping the study will be sent to the IRBs/IECs via the investigator(s), and to CBER via GSK Biologicals.

Table 24 Study holding rules

Holding rules	Event	Number/percentage of subjects
1a	Death or any life-threatening SAE.	≥ 1
1b	Any SAE that cannot reasonably be attributed to a cause other than vaccination	≥ 1
1c	Any withdrawal from the study or withdrawal from study vaccine(s)/product(s) (by investigator or subject request) following a grade 3 AE that cannot reasonably be attributed to a cause other than vaccination.	≥ 1
1d	Any local or general solicited AE leading to hospitalization, or fever > 40°C (104°F) (oral route) that cannot reasonably be attributed to a cause other than vaccination, or necrosis at the injection site, within the 7-day (Days 1-7) post-vaccination period.	≥ 1
2a	Any grade 3 solicited local AE lasting 48h or more in an investigational group, within the 7-day (Days 1-7) post-vaccination period.	≥ 30% (and ≥ 2 subjects in one group)
2b	Any grade 3 solicited general AE lasting 48h or more in an investigational group, that cannot reasonably be attributed to a cause other than vaccination, within the 7-day (Days 1-7) post-vaccination period.	≥ 20% (and ≥ 2 subjects in one group)
2c	Any grade 3 unsolicited AE in an investigational group, that cannot reasonably be attributed to a cause other than vaccination, within the 28-day (Days 1-28) post-vaccination period OR Any grade 3 abnormality in pre-specified hematological or biochemical laboratory parameters* in an investigational group, that cannot reasonably be attributed to a cause other than vaccination, within the 7 days post-vaccination.	≥ 20% (and ≥ 2 subjects in one group)

[figure not shown]
*Grading of laboratory parameters will be based on the FDA Guidance for Industry "Toxicity Grading Scale for Healthy Adult and Adolescent Volunteers Enrolled in Preventive Vaccine Clinical Trials" (refer to [APPENDIX C](#)).

[Figure 2](#) gives the probability of not meeting each holding rule 1 and 2 for 45 subjects in an investigational group. This evaluation was performed for the sample size of the initial protocol (i.e. 450 subjects, 45/group) and it was not repeated at the time of the protocol amendment 1 because of the small difference in the number of subjects per group (now 470 subjects in total, 47/group).

Each holding rule 1a-d has 80% chance of not being met for an event with a true incidence rate below 1.0% and has less than 5% of chance of not being met for an event with a true incidence rate above 7%.

Holding rule 2a has more than 90% chance of not being met for an event with a true incidence rate below 20% and has less than 52% of chance of not being met for an event with a true incidence rate above 30%.

Holding rules 2b and 2c have more than 90% chance of not being met for an event with a true incidence rate below 10% and has less than 45% of chance of not being met for an event with a true incidence rate above 20%.

Figure 2 Probability of successfully completing the study in function of adverse events incidence rates

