10.4. Determination of sample size

10.4.1. Descriptive objectives

The primary objectives of the study are to assess the reactogenicity and safety of each vaccine dose throughout the study and to describe the anti-H1 stalk immune response 28 days after each priming dose.

At the time of the protocol amendment 1, it was decided to increase the sample size from 450 to 470 subjects to take into account a larger rate of non-evaluable subjects than anticipated. The power computations from the initial protocol relative to safety endpoints were not modified because of the small sample size increase (about 2 subjects per group, from 45 to 47). The immunogenicity endpoints evaluation will be done primarily on the Per-Protocol set, which is not deemed to increase (about 43 subjects per group).

[Table 25](#) shows the true proportions associated with a 90% probability to observe an event in 45 subjects (e.g. SAE, pIMD).

Table 25 True proportions associated with a 90% probability to observe a certain number of adverse events within a group (45 subjects)

True proportion	Number of adverse events observed with > 90% probability
0.049	> 0
0.083	> 1
0.114	> 2
0.142	> 3

[Table 26](#) illustrates the 95% CIs for different possible numbers of AEs within each group.

Table 26 Two-sided exact 95% confidence intervals for the true adverse event rate at different possible observed adverse event rates (45 subjects)

Observed number of adverse events	Observed adverse event proportion	95% exact confidence interval	
		Lower limit	Upper limit
0	0.000	0.000	0.079
1	0.022	0.001	0.118
2	0.044	0.005	0.152
3	0.067	0.014	0.183
4	0.089	0.025	0.212
5	0.111	0.037	0.241
10	0.222	0.112	0.371
20	0.444	0.296	0.600
30	0.667	0.511	0.800

Table 27 presents the 95% CIs for different possible rates of immunological response within each group. A rate of unevaluable subjects of 2/45 (4%) has initially been considered for the immune response post-primary vaccination. As from protocol amendment 1, a rate of non-evaluable subjects of 4/47 (9%) has been considered for the immune response post-primary vaccination.

Table 27 Two-sided exact 95% confidence intervals for the true immunological response rate at different possible observed response rates (43 evaluable subjects)

Observed number of responses	Observed response proportion	95% exact confidence interval	
		Lower limit	Upper limit
25	0.581	0.421	0.730
30	0.698	0.539	0.828
35	0.814	0.667	0.916
40	0.930	0.809	0.985

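### Section 8.8.1 puts the 80% chance of not meeting holding rules 1a-1d at 1.0% incidence; with 45 subjects it is 63.6% there, and 80% is reached only at about 0.5%

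*Protocol*

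**What the plan says.** Section 8.8.1 of the Protocol sets out the holding rules in Table 24 and then summarises how they behave.

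- **Trigger.** Rules 1a to 1d are each met by one subject or more. Rule 1a, for example, covers "Death or any life-threatening SAE".
- **Consequence.** "Upon meeting of any holding rules, further vaccination will be immediately put on hold pending safety review".
- **Basis of the probabilities.** Figure 2 "gives the probability of not meeting each holding rule 1 and 2 for 45 subjects in an investigational group". The text adds that this was computed for the initial 45 per group and that, for the later 47 per group, "it was not repeated at the time of the protocol amendment 1 because of the small difference in the number of subjects per group".
- **Statement for rules 1a to 1d.** "Each holding rule 1a-d has 80% chance of not being met for an event with a true incidence rate below 1.0"%, and each rule "has less than 5% of chance of not being met for an event with a true incidence rate above 7"%.
- **Statements for rules 2a to 2c.** Rule 2a has more than a 90% chance of not being met below 20% incidence and less than 52% above 30%. For rules 2b and 2c the figures are more than 90% below 10% and less than 45% above 20%.

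**The concern.** A rule that fires on a single case among 45 subjects is sensitive even to rare events. At 1% incidence the expected number of cases in 45 subjects is 0.45, and an 80% chance of seeing none is too high for that expectation. The stated pair of numbers therefore looked inconsistent with the stated group size and trigger.

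What is at stake is the reader's picture of how often vaccination would be paused. These rules cover death, life-threatening SAEs and SAEs with no reasonable cause other than vaccination. The sentence is the Protocol's own summary of how readily they fire.

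**Working it through.** **Inputs**

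- n = 45 subjects in one investigational group (section 8.8.1, text introducing Figure 2); 47 is the current planned group size.
- Trigger for rules 1a to 1d: at least 1 subject (Table 24).
- Triggers for rule 2: at least 30% (2a) or at least 20% (2b, 2c) of a group, and at least 2 subjects. At n = 45 these are 14 and 9 subjects.

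**Formula.** With independent subjects and true incidence p, the number of cases X is binomial(n, p). For rules 1a to 1d, P(not met) = P(X = 0) = (1 − p)^n.

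**The plan's own figures at n = 45**

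| Rule | Incidence | Calculation | Result | Stated | Agrees |
|---|---|---|---|---|---|
| 1a-1d | 7% | 0.93^45 | 3.8% | < 5% | yes |
| 2a | 20% | P(X ≤ 13) | 94.8% | > 90% | yes |
| 2a | 30% | P(X ≤ 13) | 50.9% | < 52% | yes |
| 2b, 2c | 10% | P(X ≤ 8) | 96.8% | > 90% | yes |
| 2b, 2c | 20% | P(X ≤ 8) | 44.1% | < 45% | yes |
| 1a-1d | 1.0% | 0.99^45 | **63.6%** | 80% | **no** |

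Five of the six figures reproduce, which confirms both the method and the basis of 45. Only the 80% at 1.0% fails, by about 16 percentage points.

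**Where 80% is reached.** Solving (1 − p)^45 = 0.80 gives p = 1 − 0.8^(1/45) = 0.495%. As a check, 0.995^45 = 79.8%. Inside the range the sentence covers, at 0.75%, the chance is 0.9925^45 = 71.3%.

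**Other bases tried for the 80% at 1.0%**

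- n = 47: 0.99^47 = 62.4%, with 80% reached at 0.474%.
- n = 43 to 50: from 64.9% down to 60.5%.
- All 80 Phase I subjects: 0.99^80, about 45%.
- All nine investigational groups (9 × 45 = 405): 1.7%. All 450 subjects: 1.1%.
- n = 22: 0.99^22 = 80.2%, which matches. But 0.93^22 = 20.3%, which breaks the second half of the same sentence (under 5% above 7%), and section 8.8.1 declares no such basis.
- Trigger of two or more subjects at n = 45: 92.5% at 1.0% and 16.7% at 7%, so neither half fits.

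None of the combinations of group size and trigger tried satisfies both halves of the rule 1 sentence.

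**Chance of a hold at 1.0% in one group of 45.** 1 − 0.636 = 36.4%, against the implied 1 − 0.80 = 20%.

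**The case against.** The arithmetic is not in dispute; the objections concern its weight and reading.

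- **Nothing operates on this number.** Rules 1a to 1d act on a count of one, with reporting to the sponsor within 24 hours. No decision uses the stated probability, and the error understates pauses without loosening protection. This stands, and it limits the consequence.
- **Loose wording.** The rule 1 sentence gives a flat 80%, whereas the rule 2 sentences say more than 90%. One could read it as saying that 80% is attained somewhere below 1.0%, and 0.495% would fit. The reading is weak, because the neighbouring sentences and the second half of this one are plainly bounds that apply on one side of the quoted incidence. Figure 2 is not available here, and its curve may well be right; the sentence would still be wrong.
- **36% is not the trial's chance of a pause.** Table 24 limits rules 2a to 2c to an investigational group but puts no such limit on rules 1a to 1d. If a 1% event occurred in all groups, at least one case would be almost certain (only a 1.1% chance of none among 450). This stands: 36% applies only to an event confined to one group of 45, which is the basis the section declares.
- **The rule 2 bounds are correct as disclosed.** They hold at 45, and the Protocol says openly that they were not redone for 47. That is not an error. At 47 the triggers become 15 and 10 subjects, and the two upper bounds become 55.9% (2a at 30%) and 52.9% (2b, 2c at 20%). The reason given for not repeating the evaluation is therefore thin for those two, but no correction is required.

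**Conclusion.** The concern holds. On the Protocol's declared basis of 45 subjects and a trigger of one case, the chance of not meeting a rule 1a to 1d at 1.0% incidence is 63.6%, not 80%. The 80% level belongs to an incidence of about 0.5%. Between about 0.5% and 1.0% the sentence overstates the chance of continuing without a hold, and at 1.0% the chance of a hold is about 36% where the reader is led to expect 20%.

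The result assumes independent subjects, complete data and an event confined to one group. It does not depend on the exact group size: any n from 43 to 50 gives 60.5% to 64.9%.

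This is a certain error in one sentence of a safety section and should be corrected. It has no bearing on the rules themselves, the sample size or the analyses.

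**What to change.** In the rule 1a to 1d sentence of section 8.8.1, replace 1.0% with about 0.5% and say at least 80%, so that it reads as a lower bound like the rule 2 sentences. If 1.0% is kept as the reference incidence, state a chance of at least 63% below 1.0%. A flat 64% would repeat the fault, because the chance rises as the incidence falls.

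Check the rule 1 curve in Figure 2 against the corrected sentence.

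Optionally, add a clause that the upper bounds for rule 2 are for 45 subjects and shift by several points with group size because the triggers are whole numbers, or restate them at 47 as about 56% (2a) and about 53% (2b, 2c).

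The cost is one sentence, a check of one figure and at most one added clause. The holding rules, design, sample size and analyses stay as they are.

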8.8.2. Safety monitoring

An IDMC will be established by GSK Biologicals for the purpose of monitoring the study and to provide independent, non-binding advice on safety and ethics. The IDMC will provide recommendations about stopping, holding, continuing or modifying the trial. During the whole study period, there will be regular IDMC reviews (monthly during the vaccination phases and every 6 months during the safety follow-up phases. The frequency of these reviews may be adapted upon IDMC recommendation if deemed necessary).

During the Phase I enrolment, subjects will be vaccinated one at a time, at least 60 minutes apart, with a maximum of 10 subjects per day until ~80 subjects are enrolled (i.e. to obtain treatment groups of at least 8 subjects/group):

- If no safety issue is identified upon review of the 7 days post-Dose 1 safety data (Days 1-7) of at least 60 Phase I subjects, Dose 2 will be administered to Phase I subjects.
- If no safety issue is identified upon review of the 7-day post-Dose 1 safety data (Days 1-7) of all Phase I subjects (N = ~80), Phase II enrolment will start.

Phase I subjects will be vaccinated one at the time, at least 60 minutes apart, with a maximum of 10 subjects a day. This is applicable for Dose 1 (Day 1), Dose 2 (Day 57) and Dose 3 (booster) (Month 14) of the Phase I subjects.

Phase II subjects will be enrolled and vaccinated without limitation on the number of vaccinees per day or time between consecutive subjects.

The frequency of IDMC sessions and other operational details are described in the IDMC charter. In case of a serious safety issue during the study, GSK Biologicals will inform the IDMC as well as fulfil its regulatory obligation expeditiously.

9. SUBJECT COMPLETION AND WITHDRAWAL

9.1. Subject completion

A subject who returns for the concluding visit foreseen in the protocol (Visit 12) is considered to have completed the study.

9.2. Subject withdrawal

Withdrawals will not be replaced.

9.2.1. Subject withdrawal from the study

From an analysis perspective, a ‘withdrawal’ from the study refers to any subject who did not come back for the concluding visit foreseen in the protocol.

All data collected until the date of withdrawal/last contact of the subject will be used for the analysis.

A subject is considered a ‘withdrawal’ from the study when no study procedure has occurred, no follow-up has been performed and no further information has been collected for this subject from the date of withdrawal/last contact.

Investigators will make an attempt to contact those subjects who do not return for scheduled visits or follow-up.

Information relative to the withdrawal will be documented in the eCRF. The investigator will document whether the decision to withdraw a subject from the study was made by the subject himself/herself, or by the investigator, as well as which of the following possible reasons was responsible for withdrawal:

- Serious adverse event.
- Unsolicited non-serious adverse event.
- Solicited adverse event
- Protocol violation (specify).
- Consent withdrawal, not due to an adverse event*.
- Moved from the study area.
- Lost to follow-up.
- Other (specify).

*In case a subject is withdrawn from the study because he/she has withdrawn consent, the investigator will document the reason for withdrawal of consent, if specified by the subject, in the eCRF.

Subjects who are withdrawn from the study because of SAEs/AEs must be clearly distinguished from subjects who are withdrawn for other reasons. Investigators will follow subjects who are withdrawn from the study as result of a SAE/AE until resolution of the event (see Section 8.5.1.2).

9.2.2. Subject withdrawal from study vaccines/products

A ‘withdrawal’ from the study vaccines/products refers to any subject who does not receive the complete treatment, i.e. when no further planned dose is administered from the date of withdrawal. A subject withdrawn from the study vaccines/products may not necessarily be withdrawn from the study as further study procedures or follow-up may be performed (safety or immunogenicity) if planned in the study protocol.

Information relative to premature discontinuation of the study vaccines/products will be documented on the Vaccine Administration screen of the eCRF. The investigator will document whether the decision to discontinue further vaccination/treatment was made by the subject himself/herself, or by the investigator, as well as which of the following possible reasons was responsible for withdrawal:

- Serious adverse event.
- Unsolicited non-serious adverse event.
- Solicited adverse event
- Not willing to be vaccinated
- Other (specify).

9.3. Extension study

During the study conclusion visit, the investigator will ask each subject if they are interested to participate in a long-term study. If a subject is not interested in participating in the long-term study, the reason for refusal will be documented in the subject’s eCRF.

9.4. Screening failures

Only applicable for Phase I subjects: Screening and baseline failures are defined as subjects who withdraw or are withdrawn from the study after giving informed consent, but before receiving the study vaccine at Day 1. Data reported to the eCRF for these subjects will be limited to:

- ICF information,
- Demographic data,
- Inclusion/exclusion criteria,

- Blood sampling for hematology/biochemistry (if performed).
- Screening conclusion and study conclusion data.

Medical history, physical examination, height, weight and vital signs data, and history of previous influenza vaccination do not need to be reported to the eCRF.

10. STATISTICAL METHODS

10.1. Primary endpoints

Reactogenicity and safety

- Occurrence of solicited local and general AEs after each vaccination:
 - Occurrence of solicited local AEs during a 7-day follow-up period (i.e. on the day of vaccination and 6 subsequent days) after each vaccine dose, in all vaccine groups.
 - Occurrence of solicited general AEs during a 7-day follow-up period (i.e. on the day of vaccination and 6 subsequent days) after each vaccine dose, in all vaccine groups.
- Occurrence of unsolicited AEs after each vaccination:
 - Occurrence of unsolicited AEs during a 28-day follow-up period (i.e. on the day of vaccination and 27 subsequent days) after each vaccine dose, in all vaccine groups.
- Occurrence of hematological and biochemical laboratory abnormalities after each vaccination:
 - Any hematological (red blood cells, white blood cells and differential count, platelets count and hemoglobin level) or biochemical (alanine aminotransferase, aspartate aminotransferase, creatinine, blood urea nitrogen [BUN] and BUN-to-creatinine ratio) laboratory abnormality at each visit subsequent to Day 1, in all vaccine groups.
- Occurrence of MAEs, pIMDs and SAEs:
 - Occurrence of MAEs, pIMDs and SAEs throughout the entire study period, in all vaccine groups.

Immunogenicity

Anti-H1 stalk immune response measured by ELISA and by MN assay 28 days after each priming dose:

- Levels of anti-H1 stalk antibody titers by ELISA and by MN assay.

The following aggregate variables will be calculated for the above parameters with 95% confidence interval (CI):

- Seropositivity rates and geometric mean titers (GMTs) at Days 1, 29 and 85.

- Percentage of subjects with a \geq 4-fold increase from Day 1 to Days 29 and 85.
- Percentage of subjects with a \geq 10-fold increase from Day 1 to Days 29 and 85.
- Mean geometric increase (MGI) from Day 1 to Days 29 and 85.

